## **5.4. Treatment Assignment Procedures**

### **5.4.1. Randomization Procedures**

Randomization on the study occurs when the diagnosis of congenital CMV infection is confirmed, and the subject then is assigned to either receive 6 weeks of oral valganciclovir or 6 weeks of placebo. Study subjects will be stratified according to age at randomization (1 through 11 months, 12 through 23 months, 24 through 35 months, and  $\geq 36$  months) and CMV involvement (symptomatic and asymptomatic at birth) as a marker of disease severity. Age stratification is justified by the differences in the hearing assessments methods utilized for infants younger than 12 months versus toddlers 12 months and older. Dropouts and subjects with audiology assessments that are inadequate for study comparison will be replaced (up to 20%, or n=10).

Randomization will be implemented by the web-based randomization system developed and maintained at the UAB Biostatistics Unit at the University of Alabama at Birmingham. The generation and maintenance of study randomization codes will be the responsibility of the UAB Biostatistical Unit. The codes will be kept in a secure location in the Biostatistics Unit.

### **5.4.2. Masking Procedures**

Study subjects, investigators, and staff interacting with the study subjects will be masked to treatment. At the time of randomization, the site study pharmacist (who will not be masked to treatment) will prepare oral valganciclovir or oral placebo for distribution to the study subject. To ensure masking of all other study staff and families, study drug will be dispensed in amber bottles, along with amber-colored syringes for drawing up all doses. Additionally, the central audiologist who analyzes the audiology data will be masked to study assignment, as will all personnel at the UAB Central Unit (with the exception of the UAB Study Statistician).

Upon completion of the six month follow-up period for all study subjects, or if the study is stopped early for any reason, the study will be unmasked after all enrolled study participants have completed the Month 6 follow-up assessments and the database is frozen. In an emergency situation, in which knowledge of the treatment assignment will be used to reduce/remove an immediate hazard to a volunteer, the study PI and/or a local site PI will have the ability to access the treatment assignment. In this situation (emergency unblinding) the study/local PI must explain and justify the nature of the event that resulted in the decision to

immediately unblind to the DMID Medical Monitor and the Protocol Chair as soon as possible. This justification will be documented as a protocol deviation, and the IRBs and regulatory agencies will be informed as is appropriate.

Unmasking/Unblinding may also occur when the safety of a study participant is in question. In non-emergency situations, a conference call will be held to determine whether or not unmasking of an individual study subject is necessary or appropriate. The conference call will include the Protocol Chair, Protocol Statistician, DMID Medical Monitor and Clinical Project Manager.

#### **5.4.3. Reasons for Withdrawal Before Randomization**

The criteria for discontinuation of study participation following enrollment and before randomization include:

- Failure to confirm congenital CMV infection
- Study subject (parent/legal guardian) wishes to withdraw
- Trial termination (by UAB Central Unit, FDA, DMID, NIAID, NIH, UCL, or agreement of all investigators) issued per safety or efficacy criteria
- Any other reason which, in the opinion of the investigator, precludes the study subject's participation in the study. The principal investigator must call the Protocol Chair (or designee) prior to discontinuing a study subject for this reason.

#### **5.4.4. Reasons for Withdrawal After Randomization and During Treatment**

The criteria for discontinuations during the treatment portion of the study include:

- Development of a related serious adverse event warranting withdrawal of therapy
- Study subject (parent/legal guardian) wishes to withdraw
- Non-compliance with study procedures or medication schedule that in the opinion of the investigator warrants withdrawal
- Deterioration in general condition for which alternative treatment is indicated and which, in the opinion of the investigator, warrants withdrawal
- Trial termination (by UAB Central Unit, FDA, DMID, NIAID, NIH, UCL, or agreement of all investigators) issued per safety or efficacy criteria

- Any other reason which, in the opinion of the investigator, precludes the study subject's participation in the study. The principal investigator must call the Protocol Chair (or designee) prior to discontinuing a study subject for this reason.

#### **5.4.5. Reasons for Withdrawal After Randomization and After Completion of Treatment**

Criteria for discontinuing study subjects from the study after completion of the study medication are:

- Study subject (parent/legal guardian) wishes to withdraw
- Any other reason, which in the opinion of the investigator, should preclude the study subject's continued participation in the study. The investigator must call the Protocol Chair (or designee) prior to discontinuing a study subject for this reason.
- Any subject that is terminated due to loss to follow-up will be considered as withdrawn

#### **5.4.6. Handling of Withdrawals**

Study subjects may withdraw voluntarily from participation in the study at any time. Up to 20% (n=10) over-enrollment is allowed to replace subjects who drop-out or who have inadequate audiology assessments. Study subjects also may withdraw voluntarily from receiving the study intervention for any reason. If a study subject withdraws or is discontinued from the study at any time prior to completion of the study, the reason for this decision will be recorded on the electronic case report form (eCRF). SAEs and AEs will be followed according to guidelines in Section 9. The study subject should be encouraged to complete follow-up visits as part of the intent to treat group.

Should a study subject's therapy be discontinued prematurely, all clinical and laboratory evaluations scheduled during the next study visit will be completed on the day the study subject is discontinued. All randomized study subjects will continue to be followed as long as possible and included in the final analysis.

Since the primary endpoint requires comparison of baseline and 6 month audiology assessments, dropouts and subjects with audiology assessments that are inadequate for study comparison (Section 11.4.1) will be replaced. Characteristics of the dropouts and those with missing outcomes will be compared to determine if there is a difference between the two treatment groups. If differences are observed, this will be included in the primary outcome reporting as a limitation.

#### **5.4.7. Termination of Study**

The ethics committees, regulatory agencies, UAB Central Unit, or NIH have the right to terminate this study at any time. Reasons for terminating the study may include, but are not limited to, the following:

- The incidence or severity of adverse events in this or other studies indicates a potential health hazard to study subjects
- Study subject enrollment is unsatisfactory.

## **6. STUDY INTERVENTION/INVESTIGATIONAL PRODUCT**

### **6.1. Study Product Description**

Valcyte Powder for Oral Solution (valganciclovir) is indicated for the treatment of CMV retinitis in adult patients with AIDS and for the prevention of CMV disease in adult and pediatric kidney, heart, and kidney-pancreas transplant recipients at high risk. Simple Syrup (Syrup, NF) will be used for the placebo for valganciclovir.

#### **6.1.1. Acquisition**

Valcyte Powder for Oral Solution (valganciclovir) will be provided for this study by Genentech/Roche. Simple Syrup (Syrup, NF) for placebo will be purchased from a commercial vendor by the site. Study supply (active drug) will be maintained in a central drug repository as designated by the UAB Central Unit until study enrollment at a site, at which time the supply of study medication will be shipped to the study site pharmacist.

#### **6.1.2. Formulation, Packaging, and Labeling**

Valcyte Powder for Oral Solution (valganciclovir) will be supplied as a white to slightly yellow powder for reconstitution. The powder is provided in a round amber glass bottle, containing 12g powder containing 5g valganciclovir free base. Upon reconstitution, the resulting oral solution contains 50 mg of valganciclovir free base per 1 mL (Total = 100 mL per bottle). The inactive ingredients for the reconstituted oral solution are mannitol, povidone K-30, sodium benzoate, fumaric acid, sodium saccharin, flavoring, and purified or sterile water. The valganciclovir oral solution formulation does not contain lactose anhydrous.

#### **Placebo for Valganciclovir**

The placebo for valganciclovir is Simple Syrup (Syrup NF), which contains 60-90% sucrose in purified water. It is supplied as the commercial preparation.

Valganciclovir and Simple Syrup (Syrup NF) will be labeled with the drug identification and dosage. The label will comply with IND regulations, the local requirements of the country in which the study is being conducted and carry the required caution statement. Blinded labeling of study product will be performed by the licensed pharmacist at the time of dispensing. Valganciclovir will be dispensed in its original bottle. Simple Syrup will be transferred to a matching amber bottle. Study products (active or placebo) will be dispensed in a new bottle at each study visit during the six weeks of study drug administration.

### **6.1.3. Product Storage and Stability**

Valganciclovir will be provided as a powder for oral solution. Dry powder is to be stored at 25°C (77°C); excursions permitted to 15°C to 30°C (59°F to 86°F). Store reconstituted oral solution at 2° to 8°C (36°F to 46°F) for no longer than 49 days. Do not freeze. Shake bottle well before using.

Simple Syrup placebo is to be stored at 2° to 8°C (36°F to 46°F) for no longer than 49 days following dispensing for the study.

## **6.2. Dosage, Preparation and Administration of Study Intervention/Investigational Product**

Valcyte Powder for Oral Solution (valganciclovir) will be prepared by a licensed pharmacist in accordance with instructions in the package insert. Placebo for valganciclovir (Simple Syrup) will be transferred from the commercial bottle to identical empty amber bottles for dispensing.

Valganciclovir should be dosed at 16mg/kg body weight, unless specific dosage adjustment conditions have been met (see Section 6.3), administered orally twice daily for 6 weeks. Placebo for valganciclovir (Simple Syrup) should be dosed using the same volume that would be required for the active dose, administered orally twice daily for 6 weeks. Dose modifications for neutropenia, thrombocytopenia, renal impairment, and hepatotoxicity are detailed in Section 6.3.

Pharmacy preparation instructions for study product can be found in the protocol-specific Manual of Procedures (MOP), including directions for the reconstitution of the valganciclovir oral solution. Once reconstituted, the oral solution must be stored under refrigeration for no longer than 49 days. Valganciclovir oral solution has been shown not to adhere to syringes or to nasogastric tubing. Valganciclovir oral solution or placebo for valganciclovir should be administered into the patient's mouth by means of a syringe, which will be amber colored and provided by the study. If the patient is unable to swallow, the study product may be administered via the syringe through a nasogastric or gastric tube.

Study product administration should be timed to precede a feeding. If the subject vomits or spits up following the dosing, re-dosing will not be allowed.

## **6.3. Modification of Study Intervention/Investigational Product for a Participant**

Bone marrow suppression secondary to CMV can mimic ganciclovir toxicity. Nevertheless, the dosage of valganciclovir will be reduced or interrupted if any of the following occur.

### **6.3.1. Neutropenia**

If the ANC reproducibly (within one week) decreases to  $\leq 500$  cells/mm^3, study drug will be held until the ANC recovers to  $> 750$  cells/mm^3, and then administration of the drug will resume at the normal dose. If the ANC again reproducibly (within one week) decreases to  $\leq 750$  cells/mm^3, the study drug dosage will be reduced by 50% and maintained there as long as the ANC remains  $> 500$  cells/mm^3. If the ANC reproducibly (within one week) decreases to  $\leq 500$  cells/mm^3 on the 50% dosage, then the study medication will be discontinued. In cases of drug interruption, treatment will not be prolonged beyond the originally scheduled 6 week treatment timeframe.

Administration of granulocyte colony stimulating factor (GCSF) is allowed. All administered GCSF doses will be recorded on the concomitant medication sheet. The decision to utilize GCSF is left to the medical discretion of the participating investigator. The parameters for dose adjustment stated above, based upon ANC, will remain in effect even if the patient is receiving GCSF.

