### **6.3.2. Thrombocytopenia**

If the platelet count at baseline was  $\geq 100,000$ /mm^3, then study drug will be held if the platelet count reproducibly (within one week) decreases to  $\leq 50,000$ /mm^3. After the platelet count increases to  $\geq 50,000$ /mm^3, study drug administration at the normal dose will resume.

If the platelet count at baseline was  $\leq 100,000$ /mm^3, then study drug will be held if the platelet count reproducibly (within one week) decreases by 50% from baseline value. After the platelet count increases above 50% from baseline value, study drug administration at the normal dose will resume. If the platelet count again reproducibly (within one week) decreases by 50%, then the study medication will be discontinued. In cases of drug interruption, treatment will not be prolonged beyond the originally scheduled 6 week treatment timeframe.

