#### **7.4.2. Day 28 ( $\pm$ 2 days)**

- Hematology safety labs (see Sections 6.3 and 8.2.1.1)
  - WBC with differential
  - Hemoglobin
  - Platelet count
- Chemistry safety labs (see Sections 6.3 and 8.2.1.2)
  - ALT
  - Total Bilirubin
  - Creatinine
- Weight and length (see Section 8.1.2)
- Verbally assess previous administration of study medication by parents/ guardians
- Adjust dose of study medication for weight change, if needed
- Adverse event assessment (see Section 8.1.3)
- Concurrent medications assessment (see Section 6.6.1)
- Virology specimen for CMV viral load (see Section 8.2.2.1)
- Pharmacokinetic specimen for ganciclovir concentration (see Section 8.2.2.2)
- Updated results of any etiological investigations for SNHL.

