#### **7.4.3. Day 42 ( $\pm$ 2 days)**

- Hematology safety labs (see Section 8.2.1.1)
  - WBC with differential
  - Hemoglobin
  - Platelet count
- Chemistry safety labs (see Section 8.2.1.2)
  - ALT
  - Total Bilirubin
  - Creatinine
- Verbally assess previous administration of study medication by parents/ guardians
- Discontinue study medication after Study Day 42 dosing complete
- Adverse event assessment (see Section 9)

- Concurrent medications assessment (see Section 6.6.1)
- Virology specimen for CMV viral load (see Section 8.2.2.1)
- Pharmacokinetic specimen for ganciclovir concentration (see Section 8.2.2.2)
- Updated results of any etiological investigations for SNHL.

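### Protocol 6.3.1 is not consistent for a second confirmed ANC of 500 or below on the resumed full dose: drug continues at half dose at a count that otherwise means hold or stop

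*Protocol*

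**What the plan says.** Protocol 6.3.1 sets three steps, each triggered by a value reproduced within one week.

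1. At an ANC of 500 or below, "study drug will be held until the ANC recovers to" above 750, "and then administration of the drug will resume at the normal dose".
2. If the ANC *again* falls to 750 or below, "the study drug dosage will be reduced by 50% and maintained there as long as the ANC remains" above 500.
3. If the ANC falls to 500 or below "on the 50% dosage, then the study medication will be discontinued".

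The section also says that these thresholds stay in force under GCSF and that an interruption does not extend the six weeks. Section 9.6.1 refers to 6.3 for stopping treatment in an individual child and adds no rule of its own. The SAP does not restate the dose-adjustment rules.

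**The concern.** Consider a child who is held for a confirmed ANC of 500 or below, recovers above 750, restarts at full dose, and then has a second confirmed ANC of, say, 400. Step 2 is the one written for a recurrence, and 400 satisfies its trigger of 750 or below. The child therefore moves to half dose without a hold. Yet step 2 keeps a child on half dose only while the ANC is above 500, and that is already untrue. Step 3 does not apply, because the child was on full dose when the count fell.

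What is at stake is dosing safety and uniform practice across 17 sites. Section 9.6.2 names neutropenia as the one laboratory toxicity that earlier trials in this programme linked statistically to treatment. An ANC below 500 is Grade 4 in Appendix B (exactly 500 is Grade 3). A site that follows the sequence gives half dose. A site that notices the failed condition may hold or stop.

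**Working it through.** No formula in the plan is involved, so the check is a trace of the rule followed by a count of what is needed to reach the disputed step.

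**Trace of 6.3.1**

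| Dose when the count falls | Confirmed ANC | Action |
|---|---|---|
| Full, first episode | 500 or below | Hold until above 750, restart at full dose |
| Full, after restart | 501–750 | Half dose; the above-500 condition is met |
| Full, after restart | 500 or below | Half dose, because 500 or below lies within 750 or below; the above-500 condition is not met |
| Half | 500 or below | Discontinue |

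Three rows share the range of 500 or below. The first holds drug and the last stops it. Only the middle one continues it, and it does so against its own condition. Sections 6.2, 6.3.2–6.3.4 and 9.6.1 and the SAP contain nothing that settles this row. The ALT rule in 6.3.4 shows that a clear recurrence rule was available: a second rise past the same threshold means discontinuation.

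**ANC results needed to reach the disputed row**

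- First fall and its repeat: 2
- Recovery above 750: 1
- Second fall and its repeat: 2
- Total: 2 + 1 + 2 = 5

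Scheduled draws after baseline that feed the dose rules: the Day 14 and Day 28 visits (Protocol 7.4.1 and 7.4.2), where the line reads "Hematology safety labs (see Sections 6.3 and 8.2.1.1". That is 2. At Day 42 (7.4.3) the line reads only "Hematology safety labs (see Section 8.2.1.1", and the same visit says "Discontinue study medication after Study Day 42 dosing complete".

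Unscheduled results needed: 5 − 2 = 3. Counting Day 42 gives 5 − 3 = 2, with little practical meaning. A second fall first seen at Day 42 would be confirmed after dosing had ended. If Day 42 is the confirming draw, its ±2-day window leaves about two days of dosing.

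**Time available (illustration only)**

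Protocol 2.1.2.1 reports, for ganciclovir recipients in the earlier neonatal intravenous trial, mean onset of Grade 3–4 neutropenia at 14.2 days (SD 12.3) and mean resolution in 12.8 days (SD 13.6). If those means carried over, recovery would fall at 14.2 + 12.8 = 27.0 days. That leaves 42 − 27.0 = 15.0 days to restart, fall again and confirm. With such wide SDs the step is reachable but tight. Section 6.3.1 itself calls for repeat values within a week, so unscheduled draws are expected.

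**The case against.** The best case for the plan is that 6.3.1 is a sequence. The word *again* makes step 2 the rule for any recurrence and confines step 1 to the first episode. A second ANC of 400 then has one action, half dose. This stands, and it disposes of a stronger claim that a reader might infer: that steps 1 and 3 give the site two contradictory orders. That claim requires *again* to have no effect, and the text does not support it. The sequence reading does not explain why drug continues at a count that required a hold the first time, or how half dose can be maintained when its stated condition has failed.

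Second, the sequence closes itself. A child who stays at 500 or below is stopped once that is confirmed on half dose, and treatment is never extended past six weeks. This also stands, and the extra exposure is likely to be short.

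Third, there are backstops. Section 9.4 presumes that on-treatment neutropenia is drug-associated, 9.5.1 lists blood dyscrasias among possible serious events, 5.4.4 allows withdrawal for a related serious event, and 9.6.2 lets the sponsor interrupt dosing at any time. A Grade 4 count would not go unmanaged. These routes are discretionary, however, and none sets an ANC threshold for this step.

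Fourth, hold-then-half-dose is one clinical choice and immediate discontinuation is another. That is fair. The need is for one stated action that agrees with the section's own thresholds.

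**Conclusion.** The point holds as a minor inconsistency in a safety rule. For a second confirmed ANC of 500 or below on the resumed full dose, 6.3.1 as naturally read continues drug at half dose at a count where it otherwise holds or stops, and where its own half-dose condition is unmet. A second fall to 501–750 is not in question.

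The step should be uncommon, and the documents give no rate for it. A reader might take the earlier trial's 14 neutropenia dose adjustments among 46 treated children, scale them to 27 × 14/46 = 8.2, and call about 8 of 27 a ceiling for this trial. The documents do not support that. The figure covers the active arm only, whereas 6.3.1 governs blinded study drug in both arms, and 9 of 43 untreated children (21%) in that trial also had Grade 3–4 neutropenia. The earlier trial's dose-adjustment rules are not given either.

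A reader might also extend the criticism to platelets, because the recurrence stop in 6.3.2 sits in the paragraph for low baseline counts. That is not part of this point. Hold-and-resume for the higher-baseline group is a permissible choice, a stop rule there would be a new clinical rule, and the hold and resume limits overlap only at exactly 50,000.

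No efficacy, power or sample-size figure changes. The conclusion rests on the protocol and SAP text. The Manual of Procedures is not among the documents, so whether it gives sites a clearer instruction cannot be checked.

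**What to change.** In Protocol 6.3.1, limit the first sentence to the first episode and add: *If a second confirmed ANC on full dose is 500 or below, hold until it is above 750, then resume at 50%; if it is 501–750, reduce to 50% without a hold.* Leave the discontinuation sentence for the 50% dose unchanged. If the sponsor prefers to discontinue at a second confirmed 500 or below, that also removes the inconsistency, provided it is written down.

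The cost is a sentence or two in a short amendment and a memo to sites, with no added visits, samples or data. The downside is slightly less drug exposure in a few children, because a hold is not made up by longer treatment.

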### **6.3.2. Thrombocytopenia**

If the platelet count at baseline was  $\geq 100,000$ /mm^3, then study drug will be held if the platelet count reproducibly (within one week) decreases to  $\leq 50,000$ /mm^3. After the platelet count increases to  $\geq 50,000$ /mm^3, study drug administration at the normal dose will resume.

If the platelet count at baseline was  $\leq 100,000$ /mm^3, then study drug will be held if the platelet count reproducibly (within one week) decreases by 50% from baseline value. After the platelet count increases above 50% from baseline value, study drug administration at the normal dose will resume. If the platelet count again reproducibly (within one week) decreases by 50%, then the study medication will be discontinued. In cases of drug interruption, treatment will not be prolonged beyond the originally scheduled 6 week treatment timeframe.

